6.1.6 Physical Examination

Participants will undergo physical examination, as indicated in the Schedule of Assessments ([Table 1](#)).

The complete physical examination will include assessments of the standard physical examination items, including general appearance, skin, eyes, ears, nose, throat, head and neck, heart, chest and lungs, abdomen, extremities, lymph nodes, musculoskeletal, neurological, and other body systems, if applicable, for describing the status of the participant's health.

Investigators should pay special attention to clinical signs related to previous serious illnesses. Any new abnormalities or worsening of existing abnormalities should be reported as AEs, as appropriate (see [Section 8](#)).

6.1.7 Pregnancy Test

At Screening, female participants will perform a urine pregnancy. Regardless of the test result (positive or negative), the participant will remain eligible for study participation. Thus, the participant will remain eligible in case of positive pregnancy test. However, medical costs associated with the pregnancy will not be covered by the Sponsor, as the risk to participants has been considered non-significant (see [Appendix II](#)).

6.1.8 Identification

At the screening, after eConsent form signature, a unique identification number will be assigned to each participant. The participant will be referenced by this ID throughout the study. The study manual of procedures describes the identification assignation in full.

6.2 Study Visits (Days 1, 29, 57, and 85)

The Day 1 Visit will occur at the clinical site and subsequent visits on Study Days 29, 57, and 85 will occur remotely. On Day 1, participants will be provided and trained on an eDiary that will allow them to record their symptoms (Symptom questionnaire) and usability (Tasso user questionnaire). The eDiary entries will be reviewed at each visit and any recorded symptoms will be entered into the electronic data capture (EDC) database.

Participants will complete the user questionnaire (available in eDiary), provided by Tasso, immediately following each Tasso+™ device administration. The user questionnaire consists of questions about their user experience including assessing their willingness to use the Tasso+™ device repeatedly and at what frequency, any pain or discomfort experienced, their preference to venipuncture and finger-sticks, the ease of comprehension of the instructions and training, and the healing of the collection site.

Venous blood will be obtained from participants at the clinical site on Day 1 using syringe or Vacutainers, as described in the Schedule of Assessments ([Table 1](#)). Heart rate and blood pressure measurements should be taken in the supine position, preceded by at least 5 minutes of rest. Body temperature will be taken by ear/tympanic/temporal, oral, or forehead method.

Clinician supervised collection of blood using the Tasso+™ device will be performed at Day 1 Visit and collection of blood using the Tasso+™ device will be performed remotely on Day 29 (proctor-supported) and on Day 57 (intended to be unsupported). There will be two collections, one from each arm; left upper arm will be preferably used for serum preparation (Tasso+™/SST capillary collection tube with gold cap, see [Table 2](#)) and right upper arm will be preferably used to collect whole blood (Tasso+™/EDTA capillary collection tube with lavender cap, see [Table 2](#)). During Visits 2 and 3 (Days 29 and 57), Tasso+™ device will be self-administered by the participant. On Day 29, the self-collection will be supported by a proctor (during working hours). On Day 57, self-collection may be additionally supported by a proctor to guide the participant through the process and help to troubleshoot any difficulties (during working hours). Contact information will be provided to each participant in the event they have concerns or they need help while using Tasso+™ device.

On Day 1, Tasso+™ and venipuncture collection tubes will both be shipped by the Site following this visit.

On Day 29 and 57, blood will be remotely collected and shipped by the participant (proctor-supported and unsupported, respectively).

Training will consist of a detailed IFU and online video training. The detailed IFU will be provided in a separate document, and an overview of IFU is provided in [Section 7.4](#). In addition, when administering the Tasso+™ remotely, participants will receive proctor-support on Day 29 (and as requested, on Day 57), during working hours, the intent being to guide the participant through the process and to help troubleshoot should any difficulties be encountered. While assistance will be available to the participant during

Day 57 Visit, it is of interest to know whether the prior trainings on Tasso+™ administration prove adequate for this subsequent administration.

Nasopharyngeal swabs for qualitative and/or quantitative SARS-CoV-2 PCR will be performed and resulted by the Site. Nasopharyngeal swabs will be collected on Day 1 according to the site's standard operating procedures (SOP) and according to institutional and test kit manufacturer's SOP or instructions and resulted by institutional laboratory. Specimen labels will include protocol number, participant ID number, and date of collection.

6.3 Endpoint Assessments

Endpoint assessments should be completed as specified in Schedule of Assessments ([Table 1](#)).

The primary objective of the study, which is the evaluation of Tasso+™ blood collection device performance, will be assessed with regards to sample integrity (see [Section 6.3.1](#)), testing accuracy (see [Section 6.3.2](#)), and reliability (see [Section 6.3.3](#)) of the device.

The secondary objectives of the study, which are the evaluation of user experience and the surveillance for SARS-CoV-2 infection, will be assessed with regards to safety (see [Section 6.3.4](#)), tolerability (see [Section 6.3.5](#)), and usability (see [Section 6.3.6](#)) of the device as well as SARS-CoV-2 infection surveillance (see [Section 6.3.7](#)).

6.3.1 *Sample Integrity*

Sample integrity of the Tasso+™ device, as part of device performance, will be evaluated as the percentages of Tasso+™/SST and Tasso+™/EDTA samples with adequate volume and without moderate or gross hemolysis, and the percentage of Tasso+™/EDTA samples without clotting. These endpoints will be assessed on Day 1 for each cohort and on each of Days 29 and 57 for Cohorts A and B combined.

Blood collection volumes for Tasso+™ kits are ranging 400 to 600 µL for Tasso+™/SST kits and 250 to 500 µL for Tasso+™/EDTA kits. Adequate whole blood volume is defined as collected volume in accordance with the testing plan, ie, 300 µL. Desired volume is defined as adequate volume, which is doubled, ie, 600 µL, to allow retesting. The volume of blood collected with the Tasso+™ system will be measured in the Central Laboratory.

As defined by Central Laboratory SOP, the absence or presence of hemolysis is defined using the hemolytic index ([Table 5](#)). Thus, absence of moderate or gross hemolysis is defined as a hemolytic index <2.00.

Table 5 Impact of Varying Degrees of Hemolysis (Measured by Hemolytic Index) on Validity of Laboratory Results

Degree of Hemolysis	None	Slight	Moderate	Gross
Hemolytic Index	<0.3	≥0.3 and <2.0	≥2.0 and ≤5.0	>5.0
Sodium			No effect	
Potassium			Potassium results invalidated	
Chloride			No effect	
Blood urea nitrogen			No effect	
Creatinine	No effect	No effect	No effect	All results invalidated
Glucose			No effect	
Phosphate			Phosphate results invalidated	
Uric acid			No effect	
C-reactive protein			No effect	
SARS-CoV-2 serology			No effect	

Presence or absence of clotting in the Tasso+™/EDTA samples will be assessed by Central Laboratory on samples collected on Days 1, 29, and 57.

6.3.2 Testing Accuracy

Testing accuracy of the Tasso+™ device, as part of device performance, will be evaluated as (i) the correlation of SARS-CoV-2 serology between venipuncture and either Tasso+™/SST or Tasso+™/EDTA samples collected on Day 1; and (ii) the correlation of each chemistry analyte between venipuncture and Tasso+™/SST samples collected on Day 1. This endpoint will only be assessed on Day 1 for each cohort separately.

Seroconversion will be evaluated using IgG Nucleocapsid assay. A total serum (SST) or plasma (EDTA) volume of 175 µL will be necessary to cover potential retesting, if needed. Any participant who is positive for IgG Nucleocapsid assay for either matrix (SST or EDTA), will be considered SARS-CoV-2 positive.

The following chemistry analytes will be assessed for correlation between the two collection approaches (venipuncture and Tasso+™/SST) on Day 1: sodium, potassium, chloride, blood urea nitrogen, creatinine, glucose, phosphate, uric acid, and C-reactive protein.

Noteworthy, in case of long duration between sample collection and testing, there may be risks associated with inaccurate sodium, potassium, and glucose values.

If a sodium, potassium, or glucose level is determined by the PI to be possibly clinically significant, a venipuncture repeat of the test should be performed at the Investigator site for safety reasons. Testing will be performed by the Investigator site and will not be sent to the Central laboratory.

6.3.3 Reliability

Reliability of the Tasso+™ device, as part of device performance, will be measured as the percentage of device failures (failures that either occur due to inherent faulty mechanism of the device or due to user error) from Day 1 to Day 57. This endpoint will be assessed by the participant through completion of the Tasso user questionnaire (available in eDiary) immediately following each Tasso+™ administration.

A device failure due to a faulty mechanism consists of either: (i) failure in activation of the lancet; or (ii) lack of any blood collection within 5 minutes (see [Section 7.4](#)).

A device failure due to user error consists of either: (i) incorrect attachment of the capillary collection tube to the device; (ii) damage to the device or the capillary collection tube upon handling; (iii) lack of maintained seal between the device and the skin surface of the participant; or (iv) incomplete trigger of the button (not fully pressing the button once the Tasso+™ device is sealed to the skin surface) (see [Section 7.4](#)).

- An unscheduled kit may be used by the participant to re-attempt the administration after reporting the issue to the study staff, following instruction of the protocol-specific laboratory manual.

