3 STUDY ENDPOINTS

3.1 Primary Endpoints

The primary endpoints that will be evaluated to assess the Tasso+™ blood collection device performance are as follows:

Sample integrity

- Percentage of overall Tasso+™/SST samples collected that are with adequate volume and without moderate or gross hemolysis on Day 1 for each cohort and on each of Days 29 and 57 for Cohorts A and B combined
- Percentage of overall Tasso+™/EDTA samples collected that are with adequate volume, without moderate or gross hemolysis, and without clotting on Day 1 for each cohort and on each of Days 29 and 57 for Cohorts A and B combined

Testing accuracy

- Correlation of SARS-CoV-2 serology between venipuncture and Tasso+™/SST or Tasso+™/EDTA samples on Day 1 for each cohort
- Correlation of each chemistry analyte between venipuncture and Tasso+™/SST samples on Day 1 for each cohort

Reliability

- Percentage of Tasso+™ device failures from Day 1 to Day 57 (see details in [Section 6.3.3](#)), defined as:
 - failure in activation of the lancet;
 - lack of any blood collection within 5 minutes;
 - incorrect attachment of the capillary collection tube to the device;
 - damage to the device or the capillary collection tube upon handling;
 - lack of maintained seal between the device and the skin surface of the participant; or
 - incomplete trigger of the button (not fully pressing the button once the Tasso+™ device is sealed to the skin surface).

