4 STUDY PLAN

4.1 Overall Study Design and Plan

This is a Phase 1, multicenter, observational study that will evaluate the Tasso+™ device in approximately 200 male or female adult participants in an outpatient setting who are healthy or in well-compensated health at up to 5 US sites.

The Investigator will obtain electronically signed informed consent (eConsent form) from the participant before any study procedures are performed. For further details regarding the informed consent process, see [Section 11.3](#).

Each participant will be followed with a study visit in the Clinic on Day 1, and subsequent decentralized, remote study visits on Days 29, 57, and 85. The total duration of study participation is expected to be 85 ± 3 days.

On Day 1, each participant will be randomized 2:1 to either Cohort A or Cohort B. Tasso+™ blood samples of participants randomized to Cohort A will be shipped to the Central Laboratory where they will be centrifuged and aliquoted. However, Tasso+™ blood samples of participants randomized to Cohort B will be centrifuged and aliquoted at the Site prior to shipping to the Central Laboratory, following the same approach used for venipuncture blood samples.

The decentralized visit on Day 29 (Visit 2) will be remotely supported by a prescheduled proctor during working hours to support the participant's self-administration of the Tasso+™ device. For the decentralized visit on Day 57 (Visit 3), the participant will have the option to request a prescheduled proctor session during working hours to support the participant's self-administration of the Tasso+™ device.

The participant will use an electronic diary (eDiary) to report symptoms for 28 days following each Tasso+™ device administration (Symptom questionnaire) and to report on the usability of the Tasso+™ device (Tasso questionnaire) immediately following each Tasso+™ device administration (on Days 1, 29 and 57) and on Day 85. Contact information will be provided to each participant in the event they have concerns or they need help during working hours while using the Tasso+™ device.

Venous blood collection (phlebotomy) will take place on Day 1; capillary blood collections using Tasso+™ device will take place on Days 1, 29, and 57; usability data will be collected after each use of Tasso+™ device and on Day 85; reliability of the device will be collected after each use of Tasso+™ device (Days 1, 29, and 57).

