9.3 Sample Size

Sample size was not calculated on a formal statistical basis; however, Sponsor estimates that the sample size will be sufficient to sample the diversity of user experience regarding the unsupported use of Tasso™ for capillary blood collection.

Each participant will be randomized to either Cohort A or Cohort B in a 2:1 ratio. Thus, it is planned to randomize approximately 133 participants into Cohort A and approximately 67 participants into Cohort B.

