6.1 Sample Size Considerations

Sample size was not calculated on a formal statistical basis; however, the sample size of 200 is large enough to illustrate diversity of user experience regarding the unsupported use of Tasso+™ for capillary blood collection.

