9.5.2.3 Reliability

For each participant, the number of failures will be calculated by summing the instances where the device or the collection process has failed as follows:

- (i) failure in activation of the lancet
- (ii) lack of any blood collection within 5 minutes
- (iii) incorrect attachment of the capillary collection tube to the device
- (iv) damage to the device or the capillary collection tube upon handling
- (v) lack of maintained seal between the device and the skin surface of the participant
- (vi) incomplete trigger of the button (not fully pressing the button once the Tasso+™ device is sealed to the skin surface)

The total number of device usage instances will also be recorded.

The percentage of failures will be calculated as:

$$\text{Percentage of failures} = \frac{\text{Number of Instances with Failures}}{\text{Total Number of Device Usage Instances}} \times 100\%$$

Counts and percentages will be presented for participants in the FAS and PPS.

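### Primary reliability is one percentage over clinic and remote uses and over device and user causes, and no FAS analysis gives the decentralised failure rate

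*Protocol*

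**What the plan says.** Protocol 3.1 defines the endpoint over the whole period: "Percentage of Tasso+™ device failures from Day 1 to Day 57". Protocol 6.3.3 says that it covers "failures that either occur due to inherent faulty mechanism of the device or due to user error", and sorts six failure types into two faulty-mechanism types and four user-error types. Protocol 9.4.1.3 and SAP 9.5.2.3 divide instances with failures by all uses. On the denominator the SAP adds only "The total number of device usage instances will also be recorded", and on presentation "Counts and percentages will be presented for participants in the FAS and PPS". Neither document specifies a split of the primary result by visit, level of support or cause.

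The uses differ in setting. Day 1 is supervised in clinic, Day 29 is remote with a proctor, and Day 57 is remote with a proctor only on request (protocol 4.1). Sample integrity, a companion primary endpoint, is reported separately for Days 1, 29 and 57 (SAP 9.5.2.1).

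One setting-specific reliability result is planned, the exploratory Day 57 comparison of uses with and without proctor support. Protocol 9.4.3 names no analysis set for it. SAP 9.5.4.1 restricts it to the PPS, and SAP 6.3.2 admits to the PPS only participants with at least five successful administrations and no important protocol deviation.

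**The concern.** Protocol 1.1.1 sets out to evaluate the device both in clinic and in a decentralised setting, and protocol 1.2 expects the results to inform the feasibility of decentralised collection. A reader of the report will want to know how often the device fails at home. A percentage that mixes clinic and home uses does not answer that unless the two rates happen to be equal. It does not give the clinic rate either.

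The causes raise a similar problem. A faulty lancet calls for action on the device, and a badly attached tube calls for action on training. The protocol defines this distinction, but no planned summary uses it.

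The one result that does look at setting is drawn from a set whose membership depends on the outcome being measured.

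**Working it through.** **Plan's own figure.** Protocol 9.3 plans "approximately 133 participants into Cohort A and approximately 67 participants into Cohort B". From 200 at 2:1, 200 × 2/3 = 133.3 and 200 × 1/3 = 66.7, so this reproduces. The documents give no target failure rate, precision or power for reliability, so there is nothing further to reproduce.

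**Planned uses.** Protocol 4.1 plans "approximately 200 male or female adult participants", with device use on three visits. Protocol 6.2 says "There will be two collections, one from each arm". Planned uses are 200 × 2 × 3 = 1,200, of which 400 are in clinic and 800 remote, ignoring repeat kits. The clinic share is 400/1,200 = 33.3%. If 95% and 90% of remote uses at Days 29 and 57 take place (assumed), it is 400/1,140 = 35%. At 90% and 80% (assumed), it is 400/1,080 = 37%.

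**Pooled against remote rate.** Pooled = (400 × clinic rate + 800 × remote rate) / 1,200. Protocol 1.2 cites a study with 94.5% supervised and 93.4% unsupervised collection success, so failure is 100 − 94.5 = 5.5% and 100 − 93.4 = 6.6%. These are participant-level success rates from another study, so they are proxies only. A second cited study had 30% of participants without an adequate sample, which is used here as the top of the assumed range.

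| Clinic | Remote | Pooled | Pooled minus remote (points) | Basis |
|---|---|---|---|---|
| 5.5% | 6.6% | (2,200 + 5,280)/1,200 = 6.23% | −0.37 | cited proxies |
| 5.5% | 10% | (2,200 + 8,000)/1,200 = 8.50% | −1.50 | remote assumed |
| 5.5% | 20% | (2,200 + 16,000)/1,200 = 15.17% | −4.83 | remote assumed |
| 5.5% | 30% | (2,200 + 24,000)/1,200 = 21.83% | −8.17 | remote assumed |
| 6.6% | 6.6% | 6.60% | 0 | equal rates |
| 10% | 5% | (4,000 + 4,000)/1,200 = 6.67% | +1.67 | first use worse, both assumed |

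**Effect of the PPS on the Day 57 split.** Assume six independent uses with a common failure rate p, and treat an unsuccessful administration as a failure. A participant enters the PPS with no failure, probability (1−p)^6, or with one, probability 6p(1−p)^5. The failure rate per use within the PPS is p(1−p)^5 / [(1−p)^6 + 6p(1−p)^5] = p/(1 + 5p).

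- p = 6.6%: 0.066/1.33 = 5.0%
- p = 10%: 0.10/1.50 = 6.7%
- p = 20%: 0.20/2.00 = 10.0%
- p = 30%: 0.30/2.50 = 12.0%

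The shortfall grows with the true failure rate, so the table is least informative when failure is common.

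**The case against.** The strongest reply is that the analysis matches the endpoint as defined, the study is descriptive with no hypothesis testing (SAP 9.5.1), and clinic use is part of the stated aim, so including Day 1 is legitimate. All of this stands. It supports keeping the pooled figure, but it does not supply the missing breakdown.

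Four stronger readings go beyond the documents.

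- A reader might infer that clinic uses must dilute the decentralised rate. That holds only if they fail less often. The only paired rates cited put the gap at about 0.4 points, and because Day 1 is the first use, learning could reverse it.
- A reader might compare Day 57 alone with the pooled figure. With assumed rates of 2%, 5% and 10%, pooled is 17/3 = 5.67% and Day 57 is 1.8 times that. But Day 29 is remote too. The remote rate is (5 + 10)/2 = 7.5%, or 1.32 times pooled. Nor is Day 57 wholly unsupported, since a proctor is available on request.
- A reader might take the SAP 6.1 phrase "large enough to illustrate diversity of user experience regarding the unsupported use" to make unsupported failure the target of this endpoint. That sentence concerns user experience, and protocol 1.1.1 places reliability under device performance.
- A reader might conclude that the causes cannot be separated at all. The six types map onto the two causes in protocol 6.3.3, and SAP 9.6.2 lists device deficiencies. What is missing is a summary. The split will also be imperfect, because failures are reported by participants and absence of blood within five minutes is classed as a faulty mechanism whatever its origin.

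**Conclusion.** The point holds as a reporting gap. Followed as written, the plan yields no FAS failure rate for remote use and no summary by cause. Its only setting-specific figure covers Day 57 alone and is biased low by selection on the outcome.

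The size of the discrepancy is not known in advance. It is about 0.4 points on the cited proxies, 1.5 to 8.2 points if remote failure is assumed to be 10% to 30% with 5.5% in clinic, zero if the rates agree, and of opposite sign if first use in clinic is worse. These figures assume full attendance and no repeat kits. The PPS figures also assume independent uses with a common failure rate. The documents do not show that the pooled figure will understate remote failure; they show that the plan cannot reveal whether it does.

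**What to change.** Keep the pooled percentage as the primary result. Add to SAP 9.5.2.3, in the FAS, failure counts and percentages by visit (Days 1, 29 and 57) and by faulty mechanism versus user error as protocol 6.3.3 defines them, with 95% confidence intervals that allow for several uses per participant. In SAP 9.5.4.1, run the Day 57 reliability split by support actually used in the FAS instead of only in the PPS. This also removes the difference from protocol 9.4.3.

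The cost is one descriptive table. The questionnaire is completed after each use (protocol 6.3.3), and SAP 9.3.1 already tabulates proctor use by visit, so no new data should be needed. The sample size does not change, and no multiplicity issue arises.

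There are two limits. Some cells will be small: at 6.6% failure, 400 uses per visit give about 26 failures and a Wilson interval of roughly 4.6% to 9.5% before clustering, and the split by cause will be thinner. The Day 57 support groups are self-selected, so that comparison describes the groups and does not estimate the effect of support.
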